3.8.2. Analysis Windows

Subject visits might not occur on protocol-specified days. Therefore, for the purpose of analysis, observations will be assigned to analysis windows.

In general, the baseline value will be the last nonmissing value on or prior to the first dose date of study drug.

HCV RNA, vital signs, and safety laboratory data collected up to the last dose date + 3 days are considered to be on-treatment data and HCV RNA, vital signs, and safety laboratory data collected after the last dose date + 3 days are considered posttreatment data. The analysis windows for on-treatment HCV RNA, vital signs and safety laboratory data are provided in [Table 3-1](#).

Table 3-1. Analysis Windows for On-treatment HCV RNA, Vital Signs and Safety Laboratory Data

Nominal Visit	Cohort 1: Subjects Without Cirrhosis					
	Group 1 (LDV/SOF 12 Weeks)			Group 2 (LDV/SOF+RBV 12 Weeks)		
	Nominal Day	Lower Limit	Upper Limit	Nominal Day	Lower Limit	Upper Limit
Baseline	1	(none)	1	1	(none)	1
Week 1	7	2	11	7	2	11
Week 2	14	12	21	14	12	21
Week 4	28	22	42	28	22	42
Week 8	56	43	70	56	43	70
Week 12	84	71	≥ 85	84	71	≥ 85

Nominal Visit	Cohort 2: Subjects With Cirrhosis					
	Group 3 (LDV/SOF+RBV 12 Weeks)			Group 4 (LDV/SOF 24 Weeks)		
	Nominal Day	Lower Limit	Upper Limit	Nominal Day	Lower Limit	Upper Limit
Baseline	1	(none)	1	1	(none)	1
Week 1	7	2	11	7	2	11
Week 2	14	12	21	14	12	21
Week 4	28	22	42	28	22	42
Week 8	56	43	70	56	43	70
Week 12	84	71	≥ 85	84	71	98
Week 16	NA			112	99	126
Week 20	NA			140	127	154
Week 24	NA			168	155	≥ 168

HCV RNA, vital sign, and safety laboratory data collected after the last dose date + 3 days will be assigned to the posttreatment follow-up (FU) visit. Visit windows will be calculated from the last dose date (ie, FU Day = collection date minus the last dose date) as shown in [Table 3-2](#).

Table 3-2. Analysis Windows for Posttreatment HCV RNA, Vital Signs and Safety Laboratory Data

Nominal FU^a Visit	HCV RNA			Vital Signs and Safety Laboratory Data^b		
	Nominal FU Day	Lower Limit	Upper Limit	Nominal FU Day	Lower Limit	Upper Limit
FU-4	28	21	69	28	4	30
FU-12	84	70	146	84	31	146
FU-24	168	147	210	168	147	210

a FU-x visit = posttreatment Week-x follow-up visit.

b Vital signs and safety labs will only be summarized for the FU-4 visit (up to 30 days after last dose), the time windows after FU-4 was for listing purpose only.

3.8.3. Selection of Data in the Event of Multiple Records in an Analysis Window

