7.1.5. Treatment-Emergent Adverse Events

7.1.5.1. Definition of Treatment-Emergent

Treatment-emergent adverse events (TEAEs) are defined as one or both of the following:

- Any AEs with an onset date on or after the study drug start date and no later than 30 days after permanent discontinuation of study drug
- Any AEs leading to premature discontinuation of study drug.

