7.1.5.2. Incomplete Dates

If the onset date of AE is incomplete, then the month and year (or year alone if month is not recorded) of onset determine whether an AE is treatment emergent, as long as the AE stop date is not prior to the first dose date of study drug. The event is considered treatment emergent if both of the following 2 criteria are met:

- The AE onset and end dates are the same as or after the month and year (or year) of the first dose date of study drug
- The AE onset date is the same as or before the month and year (or year) of 30th day after the date of the last dose of study drug

An AE with a completely missing onset and stop dates, or with the onset date missing and a stop date later than the first dose date of study drug, will be considered to be treatment-emergent.

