7.1.6. Summaries of Adverse Events and Deaths

A brief high-level summary of TEAEs will be provided by treatment group for each cohort and overall and by the number and percentage of subjects who had the following: any AE, any AE of Grade 3 or above, any treatment-related AE, any treatment-related AE of Grade 3 or above, any SAE, any treatment-related SAE, any AE that led to premature discontinuation of any study drug, any AE that led to premature discontinuation of LDV/SOF, any AE that led to premature discontinuation of RBV, any AE that led to modification or interruption of any study drug, any AE that led to interruption of LDV/SOF, any AE that led to modification or interruption of RBV. All deaths (including those that are treatment emergent and those that are not treatment emergent) observed during the study will also be summarized and included in this table.

Adverse event summaries will provide the number and percentage of subjects with TEAEs by SOC and PT, by treatment group in each cohort on the Safety Analysis Set as follows:

- All AEs
- AEs of Grade 3 or above
- All treatment-related AEs
- Treatment-related AEs of Grade 3 or above
- All SAEs
- All treatment-related SAEs
- AEs leading to premature discontinuation of any study drug
- Adverse Events Leading to Modification or Interruption of Any Study Drug

Multiple events will be counted once only per subject in each summary. Adverse events will be summarized and listed first in alphabetic order of SOC and then by PT in order of descending incidence of the overall treatment group within each SOC. In summaries by severity grade, the most severe grade will be used for those AEs that occurred more than once in an individual subject during the study.

In addition to the above summary tables, TEAEs will also be summarized by PT only, in order of descending incidence within the overall treatment group for:

- AEs that occurred in at least 5% of subjects within any treatment group
- AEs of Grade 3 or above
- All treatment-related AEs
- All SAEs
- AEs leading to premature discontinuation of any study drug
- AEs leading to premature discontinuation of LDV/SOF
- AEs leading to premature discontinuation of RBV (groups 2 and 3 only)
- AEs leading to premature discontinuation of all study drugs
- AEs leading to modification or interruption of any study drug
- AEs leading to modification or interruption of RBV (groups 2 and 3 only)

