A baseline laboratory value will be defined as the final assessment performed on or prior to the date/time of first dose of study drug. Change from baseline to a postbaseline visit will be defined as the visit value minus the baseline value. The mean, median, Q1, Q3, minimum, and maximum will be displayed to reported number of digits, SD to reported number of digits plus 1.

Median (Q1, Q3) of the observed values for hemoglobin and platelets will be plotted using a line plot by treatment group and visit.

In the case of multiple values in an analysis window, data will be selected for analysis as described in Section 3.8.3 (Selection of Data in the Event of Multiple Records in a Window).

The number of subjects with hemoglobin < 10 g/dL and < 8.5 g/dL at any postbaseline visits (up to 30 days after the last dose of any study drug) will be summarized by treatment group.

7.2.2. **Graded Laboratory Values**

The Gilead Grading Scale for Severity of Adverse Events and Laboratory Abnormalities will be used for assigning toxicity grades to laboratory results for analysis as Grade 0, Grade 1 (mild), Grade 2 (moderate), Grade 3 (severe), or Grade 4 (potentially life threatening). Grade 0 includes all values that do not meet criteria for an abnormality of at least Grade 1. Some laboratory tests have laboratory toxicity criteria for both increased and decreased levels; analyses for each direction (ie, increased, decreased) will be presented separately.

7.2.2.1. **Treatment-Emergent Laboratory Abnormalities**

Treatment-emergent laboratory abnormalities are defined as values that increase at least 1 toxicity grade from baseline at any postbaseline time point, up to and including the date of last dose of study drug plus 30 days for subjects who permanently discontinued study drug.

If the relevant baseline laboratory value is missing, then any abnormality of at least Grade 1 will be considered treatment emergent.

7.2.2.2. **Summaries of Laboratory Abnormalities**

Laboratory data that are categorical will be summarized using the number and percentage of subjects in the study with the given response at baseline and each scheduled postbaseline visit.

The following summaries (number and percentage of subjects) for treatment-emergent laboratory abnormalities will be provided by analyte and treatment group; subjects will be categorized according to the most severe postbaseline abnormality grade for a given analyte:

- Graded laboratory abnormalities

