- Grade 3 or above laboratory abnormalities

For all summaries of laboratory abnormalities, the denominator is the number of subjects with nonmissing postbaseline values up to 30 days after last dose of study drug for the laboratory parameter of interest.

A by-subject listing of treatment-emergent Grade 3 or above laboratory abnormalities will be provided by subject ID number and visit in chronological order. This listing will include all test results that were collected throughout the study for the analyte of interest, with all applicable severity grades or abnormal flags displayed.

7.3. **Body Weight, Height, and Vital Signs**

Vital signs (systolic and diastolic blood pressure [mmHg], pulse [beats/min]) at each visit, and change from baseline at each visit will be summarized for the Safety Analysis Set using descriptive statistics (n, mean, SD, median, Q1, Q3, minimum, and maximum) by treatment group. The baseline value will be defined as the last available value collected on or prior to the date/time of first dose of study drug. Change from baseline to a postbaseline visit will be defined as the postbaseline value minus the baseline value.

In the case of multiple values in an analysis window, data will be selected for analysis as described in Section 3.8.3 (Selection of Data in the Event of Multiple Records in a Window). No inferential statistics will be generated.

A by-subject listing of vital signs (systolic and diastolic blood pressure [mmHg], pulse [beats/min], respiration [breaths/min], and body temperature [°C]) will be provided by subject ID number and visit in chronological order. In the same manner, a by-subject listing of body weight, height, and BMI will be provided separately.

7.4. **Prior and Concomitant Medications**

Medications collected at Screening and during the study will be coded using the current version of the World Health Organization (WHO) Drug dictionary. The medications will be categorized as prior, concomitant, or both using the following definitions:

- Prior medications: any medications taken prior to the initial study drug dosing date
- Concomitant medications: any medications initially taken on or after the initial study drug dosing date and within the study drug's treatment period (including study drug's therapeutic reach).

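### In Cohort 2, crude safety incidences are counted over a planned 114 days in Group 3 and 198 days in Group 4, and no planned table puts the two groups on a common period

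*SAP*

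**What the plan says.** SAP Section 7.1.6 plans crude counts and percentages: "Adverse event summaries will provide the number and percentage of subjects with TEAEs by SOC and PT, by treatment group in each cohort". A subject counts once per summary, however many events occur.

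The counting period follows from the individual definitions:

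- **TEAEs** (Section 7.1.5.1): onset from first dose and "no later than 30 days after permanent discontinuation of study drug". A second limb adds "Any AEs leading to premature discontinuation of study drug", with no date limit.
- **Partial AE onset dates** (Section 7.1.5.2): judged by month and year, with the end criterion "The AE onset date is the same as or before the month and year (or year) of 30th day" after last dose. An AE whose onset is wholly missing is treatment-emergent if its stop date is also missing or falls after first dose.
- **Hemoglobin < 10 and < 8.5 g/dL** (Section 7.2.1): subjects below each threshold "at any postbaseline visits (up to 30 days after the last dose of any study drug) will be summarized by treatment group".
- **Treatment-emergent laboratory abnormalities** (Section 7.2.2.1): "values that increase at least 1 toxicity grade from baseline at any postbaseline time point, up to and including the date of last dose" plus 30 days. Section 7.2.2.2 classes each subject by worst grade, and "the denominator is the number of subjects with nonmissing postbaseline values up to 30 days after last dose of study drug".

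Section 1.2 sets 12 weeks of treatment for Group 3 and 24 weeks for Group 4. Section 1.1 makes safety with or without RBV, for 12 or 24 weeks, a primary objective, judged by review of the accumulated data.

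**The concern.** A percentage based on each subject's first event or worst grade cannot fall as the counting period lengthens, apart from trivial changes in a laboratory denominator. In Cohort 2 the longer period belongs to the arm without RBV. Background events that have nothing to do with either regimen are therefore counted for 84 more planned days in Group 4 than in Group 3.

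Groups 3 and 4 are the only randomized contrast in cirrhotic subjects. Someone reading their columns side by side cannot tell how much of a difference, or of an apparent absence of difference, comes from RBV and how much from counting time. An excess under RBV could be hidden. Cohort 1 does not have this problem, because both groups have the same planned window, but it covers non-cirrhotic subjects only (16 and 17 by actual treatment, Section 6.4.2).

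**Working it through.** **Inputs.** Last planned treatment days are Day 84 and Day 168 (Section 4.2.1). The 30-day extension comes from Sections 7.1.5.1, 7.2.1 and 7.2.2.1. Subjects by actual treatment are 25 in Group 3 and 24 in Group 4 (Section 6.4.2). The draw schedule is in Appendix 2.

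**1. Planned windows.** The SAP does not state the totals, but its rules give them.

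- Group 3: 12 × 7 = 84; 84 + 30 = 114 days.
- Group 4: 24 × 7 = 168; 168 + 30 = 198 days.
- Difference 84 days; ratio 198/114 = 1.74.

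**2. Scheduled hematology and chemistry draws in the window, excluding early-termination visits.**

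- Group 3: Weeks 1, 2, 4, 8, 12 and posttreatment Week 4 = 6.
- Group 4: the same plus Weeks 16, 20 and 24 = 9.

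**3. Search for a common-period summary.** The AE, hemoglobin-threshold and graded-laboratory tables in Appendix 1 (15.11.2.x, 15.11.4.x, 15.11.5.x, 15.11.6.1.6, 15.11.6.2, 15.11.6.3) include no fixed-day cut, exposure-adjusted rate or time-to-event display. The by-visit hemoglobin table (15.11.6.1.5) compares levels at shared visits, not the number of subjects who crossed a threshold.

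**4. Possible size.** The SAP gives no event timing, so this step is assumption. Let both arms have the same daily hazard, h on Days 1-28 and k·h afterwards, and let r be the Group 3 incidence over 114 days.

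- h = −ln(1 − r) / (28 + 86k)
- Group 4 over 198 days = 1 − exp[−h(28 + 170k)]
- Either group over Days 1-87 = 1 − exp[−h(28 + 59k)]

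Example with r = 0.30, k = 1: h = 0.3567/114 = 0.00313. Group 4 = 1 − exp(−0.00313 × 198) = 0.462. Days 1-87 = 1 − exp(−0.00313 × 87) = 0.238.

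| Group 3, 114 days | Group 4, 198 days (k = 1, 0.5, 0.25, 0) | Either group, Days 1-87 (same k) | Largest gap | Largest gap × 24 |
|---|---|---|---|---|
| 10% | 16.7, 15.4, 13.9, 10.0% | 7.7, 8.2, 8.7, 10.0% | 7 points | 1.6 subjects |
| 30% | 46.2, 43.3, 39.8, 30.0% | 23.8, 25.1, 26.5, 30.0% | 16 points | 3.9 subjects |
| 50% | 70.0, 66.8, 62.7, 50.0% | 41.1, 43.0, 45.0, 50.0% | 20 points | 4.8 subjects |

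With k = 0 there is no gap. On the common period the two arms agree under every shape, as they should when their hazards are equal.

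**5. What could be masked.** Under constant hazards the crude percentages are equal when 114·h₃ = 198·h₄, that is, when the Group 3 daily hazard is 1.74 times that of Group 4. This is the upper end, because the k = 0 pattern masks nothing.

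**6. Chance error.** Wald 95% half-width = 1.96 × √[r(1 − r)(1/25 + 1/24)] = 0.168, 0.257 and 0.280 at r = 0.10, 0.30 and 0.50. Each exceeds the corresponding largest gap (7, 16 and 20 points).

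**7. Where a common cut could fall.** Week 12 plus the 3-day visit window is Day 84 + 3 = Day 87. Section 3.8.2 supports the same day: "safety laboratory data collected up to the last dose date + 3 days are considered to be on-treatment data", so Day 87 is the last on-treatment laboratory day for a Group 3 subject dosed to Day 84. Up to nominal Week 12 both groups have 5 scheduled draws (Weeks 1, 2, 4, 8, 12).

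**The case against.** The strongest reply is that nothing here is wrong. Cohort 2 randomizes whole regimens, duration is part of each regimen, and events in the extra 84 days are part of what Group 4 experiences. Safety is descriptive by group, and the SAP's between-group tests concern SVR12. That stands. A reader might infer that the crude tables are invalid, or that the SAP undertakes to attribute Group 3 versus Group 4 safety differences to RBV. The text supports neither: the objective is to evaluate safety by review of the accumulated data.

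Planned output also covers part of the need. Hemoglobin and platelets are summarized and plotted at shared visits, exposure is tabulated by group (Table 15.11.1), and the AE and laboratory listings for 49 subjects would let a reader rebuild a cut by hand. This narrows the gap without closing it, since levels at a visit are not incidence and listings are not a summary. The RBV-specific AE tables (Groups 2 and 3 only) are not affected.

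The size argument is fair as well. The hazard shapes are assumed, every range begins at zero, and the largest gaps lie below chance error. The possible shift nevertheless runs in one direction and can be foreseen.

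A fixed cut has a weakness of its own. Under Section 7.1.5.2 an AE with wholly missing onset can be treatment-emergent if it stops any time after first dose. Without a further rule, a Group 4 event from after Day 87 could enter the common-period table.

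**Conclusion.** The point holds as a one-directional limit on interpretation, not as an error. The crude Cohort 2 incidences describe each whole regimen correctly, over planned windows of 114 and 198 days, but no planned table compares the groups over a common period. Longer counting can raise the Group 4 figure or leave it unchanged. It can therefore hide a Group 3 excess but cannot create one.

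A reader might infer a definite bias of, say, 16 points. The SAP does not support that. With equal hazards and a Group 3 incidence of 10% to 50%, the gap is anywhere from 0 to 20 points depending on event timing, and it is below chance error with 25 and 24 subjects. The 114 and 198 days are planned values and shorten with early discontinuation.

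This is an improvement to consider, with medium confidence.

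**What to change.** 1. Keep the crude tables. Footnote the Cohort 2 and overall columns to say that planned counting windows differ (114 versus 198 days).
2. Add one supplementary descriptive table for Groups 3 and 4. Include the brief-summary TEAE categories that apply to both groups (omitting the RBV-specific rows), graded laboratory abnormalities and the two hemoglobin thresholds. Restrict it to events or samples that already qualify under the existing treatment-emergent or 30-day rules and whose onset or collection falls on Day 1 through Day 87. Apply the same cut to AEs leading to discontinuation.
3. Handle partial AE onset dates by the month/year rule of Section 7.1.5.2, with Day 87 as the end date.
4. Count an AE with wholly missing onset in this table only if its stop date is on or before Day 87. Give the number of all other missing-onset AEs by group in a footnote.

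The cost is one table and a footnote, from dates already collected. The downside is small counts. Events after Day 87 appear only in the crude tables, including posttreatment Week 4 samples and Group 4 samples from Days 88-98, which Table 3-1 assigns to Week 12.

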7.5. Electrocardiogram Results

ECG examination is only conducted at baseline visit, a summary of the investigators' assessment of ECG results at baseline will be presented by treatment group for each cohort using the following categories: normal; abnormal, not clinically significant; abnormal, clinically significant; or missing. The number and percentage of subjects will be presented.

A by-subject listing for ECG assessment results at baseline will be provided by subject ID number.

7.6. Other Safety Measures

A data listing will be provided for subjects who become pregnant during the study.

7.7. Changes From Protocol-Specified Safety Analyses

There are no deviations from the protocol-specified safety analyses.

9. SOFTWARE

SAS® Software Version 9.2 or higher. SAS Institute Inc., Cary, NC, USA.

10. SAP REVISION

Revision Date (DD MMM YYYY)	Section	Summary of Revision	Reason for Revision

11. APPENDICES

- Appendix 1. Table of Contents for Statistical Tables, Figures, and Listings
- Appendix 2. Schedule of Assessments
- Appendix 3. QOL Score Calculation Algorithms

Appendix 1. Table of Contents for Statistical Tables, Figures, and Listings

Table Number	Title	Analysis Set
15.8.1.1	Subjects Randomized and Treated by Country and Investigator	Safety Analysis Set
15.8.1.2	Subjects Randomized and Treated by Randomization Stratum	Safety Analysis Set
15.8.1.3	Subject Disposition	Screened Subjects
15.8.1.4	Reasons for Screen Failure	Screened Subjects
15.8.3.1	Demographics	Safety Analysis Set
15.8.3.2	Demographics	Full Analysis Set by Randomized Treatment
15.8.3.3	Baseline Characteristics	Safety Analysis Set
15.8.3.4	Baseline Characteristics	Full Analysis Set by Randomized Treatment
15.8.3.5	Baseline Fibrosis Stage	Safety Analysis Set
15.8.3.6	Baseline Fibrosis Stage	Full Analysis Set by Randomized Treatment
15.8.3.7	Medical History	Safety Analysis Set
15.8.4	Adherence to Study Drug	Safety Analysis Set
15.9.1.1	SVR12	Full Analysis Set by Randomized Treatment
15.9.1.2	SVR12	Full Analysis Set by Actual Treatment
15.9.2.1.1	Virologic Outcomes	Full Analysis Set by Randomized Treatment
15.9.2.1.2	Virologic Outcomes	Full Analysis Set by Actual Treatment
15.9.2.1.3	Virologic Outcomes by Subgroup	Full Analysis Set by Randomized Treatment
15.9.2.1.4	Virologic Outcomes by Subgroup	Full Analysis Set by Actual Treatment
15.9.2.1.5	Virologic Outcomes by Visit During Posttreatment Follow Up	Full Analysis Set by Randomized Treatment
15.9.2.1.6	Virologic Outcomes by Visit During Posttreatment Follow Up	Full Analysis Set by Actual Treatment
15.9.2.2	SVR by Visit During Posttreatment Follow Up	Full Analysis Set by Randomized Treatment
15.9.2.3	SVR by Visit During Posttreatment Follow Up	Full Analysis Set by Actual Treatment
15.9.2.4	Concordance Between SVR12 and SVR24	Full Analysis Set by Randomized Treatment

Table Number	Title	Analysis Set
15.9.2.5	Proportion of Subjects with HCV RNA Less than LLOQ While on Treatment by Visit	Full Analysis Set by Randomized Treatment
15.9.2.6	HCV RNA (log ₁₀ IU/mL) and Change from Baseline by Visit Through End of Treatment	Full Analysis Set by Randomized Treatment
15.9.4.1	SVR12 by Subgroup	Full Analysis Set by Randomized Treatment
15.9.4.2	SVR12 by Subgroup	Full Analysis Set by Actual Treatment
15.9.4.3	SVR12 by Early Viral Response	Full Analysis Set by Randomized Treatment
15.9.4.4	SVR12 by Early Viral Response	Full Analysis Set by Actual Treatment
15.9.4.5	SVR12 by Dose Modifications	Full Analysis Set by Randomized Treatment
15.9.4.6	SVR12 by Dose Modifications	Full Analysis Set by Actual Treatment
15.9.4.7	SVR12 by Randomization Strata	Full Analysis Set by Randomized Treatment
15.9.4.8	SVR12 by Randomization Strata	Full Analysis Set by Actual Treatment
15.11.1	Duration of Exposure to Study Regimen	Safety Analysis Set
15.11.2.1.1	Adverse Events: Brief Summary	Safety Analysis Set
15.11.2.1.2	All Treatment-Emergent Adverse Events	Safety Analysis Set
15.11.2.1.3	Treatment-Emergent Adverse Events That Occurred in At Least 5% of Subjects in Any Treatment Group by Preferred Term	Safety Analysis Set
15.11.2.2.1	Treatment-Emergent Adverse Events of Grade 3 or Above	Safety Analysis Set
15.11.2.2.2	Treatment-Emergent Adverse Events of Grade 3 or Above by Preferred Term	Safety Analysis Set
15.11.2.3.1	Treatment-Emergent Treatment-Related Adverse Events	Safety Analysis Set
15.11.2.3.2	Treatment-Emergent Treatment-Related Adverse Events by Preferred Term	Safety Analysis Set
15.11.2.3.3	Treatment-Emergent Treatment-Related Adverse Events of Grade 3 or Above	Safety Analysis Set
15.11.2.4.1	Adverse Events Leading to Modification or Interruption of Any Study Drug	Safety Analysis Set
15.11.2.4.2	Adverse Events Leading to Modification or Interruption of Any Study Drug by Preferred Term	Safety Analysis Set
15.11.2.4.3	Adverse Events Leading to Modification or Interruption of RBV by Preferred Term	Safety Analysis Set

Table Number	Title	Analysis Set
15.11.4.1	Treatment-Emergent Serious Adverse Events	Safety Analysis Set
15.11.4.2	Treatment-Emergent Serious Adverse Events by Preferred Term	Safety Analysis Set
15.11.4.3	Treatment-Emergent Treatment-Related Serious Adverse Events	Safety Analysis Set
15.11.5.1	Adverse Events Leading to Premature Discontinuation of Any Study Drug	Safety Analysis Set
15.11.5.2	Adverse Events Leading to Premature Discontinuation of Any Study Drug by Preferred Term	Safety Analysis Set
15.11.5.3	Adverse Events Leading to Premature Discontinuation of LDV/SOF by Preferred Term	Safety Analysis Set
15.11.5.4	Adverse Events Leading to Premature Discontinuation of RBV by Preferred Term	Safety Analysis Set
15.11.5.5	Adverse Events Leading to Premature Discontinuation of All Study Drugs by Preferred Term	Safety Analysis Set
15.11.6.1.1	ALT (U/L) and Change from Baseline by Visit	Safety Analysis Set
15.11.6.1.2	AST (U/L) and Change from Baseline by Visit	Safety Analysis Set
15.11.6.1.3	Total Bilirubin (mg/dL) and Change from Baseline by Visit	Safety Analysis Set
15.11.6.1.4	Alkaline Phosphatase (U/L) and Change from Baseline by Visit	Safety Analysis Set
15.11.6.1.5	Hemoglobin (g/dL) and Change from Baseline by Visit	Safety Analysis Set
15.11.6.1.6	Subjects with Postbaseline Hemoglobin < 10 g/dL and < 8.5 g/dL	Safety Analysis Set
15.11.6.1.7	Reticulocytes (x 10 ³ /uL) and Change from Baseline by Visit	Safety Analysis Set
15.11.6.1.8	WBC (x 10 ³ /uL) and Change from Baseline by Visit	Safety Analysis Set
15.11.6.1.9	Neutrophils (x 10 ³ /uL) and Change from Baseline by Visit	Safety Analysis Set
15.11.6.1.10	Lymphocytes (x 10 ³ /uL) and Change from Baseline by Visit	Safety Analysis Set
15.11.6.1.11	Platelets (x 10 ³ /uL) and Change from Baseline by Visit	Safety Analysis Set
15.11.6.1.12	INR and Change from Baseline by Visit	Safety Analysis Set
15.11.6.2	Treatment-Emergent Graded Laboratory Abnormalities	Safety Analysis Set
15.11.6.3	Treatment-Emergent Grade 3 or Above Laboratory Abnormalities	Safety Analysis Set
15.11.7.1	Systolic Blood Pressure (mmHg) and Change from Baseline by Visit	Safety Analysis Set
15.11.7.2	Diastolic Blood Pressure (mmHg) and Change from Baseline by Visit	Safety Analysis Set
15.11.7.3	Pulse (bpm) and Change from Baseline by Visit	Safety Analysis Set
15.11.7.4	Concomitant Medications	Safety Analysis Set
15.11.7.5	Summary of 12-Lead ECG Assessment at Baseline	Safety Analysis Set
15.12.1.1	Summary of SF-36 Quality of Life Questionnaire	Full Analysis Set by Randomized Treatment

Table Number	Title	Analysis Set
15.12.1.2	Summary of SF-36 Quality of Life Questionnaire	Full Analysis Set by Actual Treatment
15.12.2.1	Summary of CLDQ-HCV Quality of Life Questionnaire	Full Analysis Set by Randomized Treatment
15.12.2.2	Summary of CLDQ-HCV Quality of Life Questionnaire	Full Analysis Set by Actual Treatment
15.12.3.1	Summary of FACIT-F Quality of Life Questionnaire	Full Analysis Set by Randomized Treatment
15.12.3.2	Summary of FACIT-F Quality of Life Questionnaire	Full Analysis Set by Actual Treatment
15.12.4.1	Summary of WPAI: Hep C Quality of Life Questionnaire	Full Analysis Set by Randomized Treatment
15.12.4.2	Summary of WPAI: Hep C Quality of Life Questionnaire	Full Analysis Set by Actual Treatment

Figure Number	Title	Analysis Set
15.8.1	Subject Disposition	Screened Subjects-by Randomized Treatment Group
15.8.2	Subject Disposition	Screened Subjects-by Actual Treatment Group
15.9.1	Proportion of Subjects with HCV RNA < LLOQ While on Treatment by Visit	Full Analysis Set by Randomized Treatment Group
15.9.2	Mean \pm SD Change from Baseline in HCV RNA (\log_{10} IU/mL) by Treatment Group by Visit Through End of Treatment	Full Analysis Set by Randomized Treatment
15.9.3	Median (Q1, Q3) Change from Baseline in HCV RNA (\log_{10} IU/mL) by Treatment Group by Visit Through End of Treatment	Full Analysis Set by Randomized Treatment
15.9.4	Mean \pm SD HCV RNA (\log_{10} IU/mL) by Treatment Group by Visit Through End of Treatment	Full Analysis Set by Randomized Treatment
15.9.5	Median (Q1, Q3) HCV RNA (\log_{10} IU/mL) by Treatment Group by Visit Through End of Treatment	Full Analysis Set by Randomized Treatment
15.9.6.1	Forest Plot of SVR12 by Subgroup	Full Analysis Set by Randomized Treatment
15.9.6.2	Forest Plot of SVR12 by Subgroup	Full Analysis Set by Actual Treatment
15.9.7	Forest Plot of SVR12 by Randomization Strata	Full Analysis Set by Randomized Treatment
15.10.1	Median (Q1, Q3) Hemoglobin (g/dL) by Visit	Safety Analysis Set
15.10.2	Median (Q1, Q3) Platelets ($\times 10^3$ / μ L) by Visit	Safety Analysis Set
15.11.1.1	Mean \pm SD Change from Baseline in SF-36 by Visit	Full Analysis Set by Randomized Treatment
15.11.1.2	Mean \pm SD Change from Baseline in SF-36 by Visit	Full Analysis Set by Actual Treatment
15.11.2.1	Mean \pm SD Change from Baseline in CLDQ-HCV by Visit	Full Analysis Set by Randomized Treatment
15.11.2.2	Mean \pm SD Change from Baseline in CLDQ-HCV by Visit	Full Analysis Set by Actual Treatment
15.11.3.1	Mean \pm SD Change from Baseline in FACIT-F by Visit	Full Analysis Set by Randomized Treatment
15.11.3.2	Mean \pm SD Change from Baseline in FACIT-F by Visit	Full Analysis Set by Actual Treatment
15.11.4.1	Mean \pm SD Change from Baseline in WPAI: Hep C by Visit	Full Analysis Set by Randomized Treatment

Figure Number	Title	Analysis Set
15.11.4.2	Mean +/- SD Change from Baseline in WPAI: Hep C by Visit	Full Analysis Set by Actual Treatment

Listing Number	Title	Analysis Set
16.1.1	Lot Number and Kit ID	Safety Analysis Set
16.1.2	Randomization Scheme and Code	All Randomized Subjects
16.2.1.1	Disposition for Subjects who Completed Study Treatment and Study	Safety Analysis Set
16.2.1.2	Disposition for Subjects who Did Not Complete Study Treatment and/or Study with Reasons for Premature Discontinuation of Study Treatment and/or Study	Safety Analysis Set
16.2.2.1	Inclusion and Exclusion Criteria	Subjects Not Treated
16.2.2.2	Subjects Randomized and Treated Who Did Not Meet Eligibility Criteria	Safety Analysis Set
16.2.2.3	Randomization Stratification Discrepancies Between IWRS and Database Values	Safety Analysis Set
16.2.2.4	Subjects Who Received Incorrect Study Drug Based on Randomized Treatment Assignment	Safety Analysis Set
16.2.3	Subjects Who Were Excluded from Safety and Full Analysis Sets	All Randomized Subjects
16.2.4.1	Demographics	Safety Analysis Set
16.2.4.2.1	Baseline Characteristics	Safety Analysis Set
16.2.4.2.2	Cirrhosis Determination	Safety Analysis Set
16.2.4.3.1	Medical History	Safety Analysis Set
16.2.4.3.2	Prior HCV Treatment and Response	Safety Analysis Set
16.2.4.4	Prior and Concomitant Medications	Safety Analysis Set
16.2.5.1	Study Drug Administration	Safety Analysis Set
16.2.5.2	Study Drug Accountability and Adherence	Safety Analysis Set
16.2.6.1	HCV RNA (\log_{10} IU/mL) and Change from Baseline	Safety Analysis Set
16.2.6.2	Subjects with Virologic Failure	Safety Analysis Set
16.2.6.3	Subjects with 'Other' Virologic Outcome	Safety Analysis Set
16.2.6.4	Subjects with Relapse after Posttreatment Week 12	Safety Analysis Set
16.2.6.5	SF-36 Quality of Life Questionnaire	Safety Analysis Set
16.2.6.6	CLDQ-HCV Quality of Life Questionnaire	Safety Analysis Set
16.2.6.7	FACIT-F Quality of Life Questionnaire	Safety Analysis Set
16.2.6.8	WPAI: Hep C Quality of Life Questionnaire	Safety Analysis Set
16.2.7.1	All Adverse Events	Safety Analysis Set
16.2.7.2	Adverse Events of Grade 3 or Above	Safety Analysis Set
16.2.7.3	Deaths	Safety Analysis Set

Listing Number	Title	Analysis Set
16.2.7.4	Serious Adverse Events	Safety Analysis Set
16.2.7.5	Adverse Events Leading to Premature Discontinuation of Any Study Drug	Safety Analysis Set
16.2.7.6	Adverse Events Leading to Modification or Interruption of Any Study Drug	Safety Analysis Set
16.2.8.1.1	Subjects with Postbaseline Hemoglobin < 10 g/dL and < 8.5 g/dL	Safety Analysis Set
16.2.8.1.2	Central Laboratory (Covance) Reference Ranges	Safety Analysis Set
16.2.8.1.3	Subjects with Treatment-Emergent Grade 3 or Above Laboratory Abnormalities	Safety Analysis Set
16.2.8.1.4.1	Hematology: Hematocrit, Hemoglobin, Reticulocytes, MCV, RBC, WBC, and Platelets	Safety Analysis Set
16.2.8.1.4.2	Hematology: WBC, Neutrophils, and Lymphocytes	Safety Analysis Set
16.2.8.1.4.3	Hematology: Eosinophils, Basophils, and Monocytes	Safety Analysis Set
16.2.8.1.5	Coagulation: INR and APTT	Safety Analysis Set
16.2.8.1.6	Serum Chemistry: Sodium, Potassium, Creatine Kinase, Creatinine, Estimated GFR (Cockcroft-Gault), and Glucose	Safety Analysis Set
16.2.8.1.7	Serum Chemistry: AST, ALT, Total Bilirubin, Direct Bilirubin, Alkaline Phosphatase, GGT, Albumin, and Lipase	Safety Analysis Set
16.2.8.1.8	Urinalysis: Urine Blood, Glucose, pH, Protein, Urobilinogen, and Leukocyte Esterase	Safety Analysis Set
16.2.8.2.1	Vital Signs	Safety Analysis Set
16.2.8.2.2	Height, Weight, and BMI	Safety Analysis Set
16.2.8.3	Pregnancy	Safety Analysis Set
16.2.8.4	12-Lead Electrocardiogram Results at Baseline	Safety Analysis Set

